12.1.6. Removing Cellular Matter (Opacification) between the PCIOL and IOPCL

Removal of cellular matter (opacification) between the PCIOL and IOPCL will be recorded. **Prior to recording, please ensure that the video equipment is in full working order**. Video recordings will be shared with the Sponsor and FDA.

Using an irrigating cannula and BSS loosen the cortical/cellular material between the two lenses from the periphery, followed by removal with a coaxial/aspiration (I/A handpiece). Alternatively utilize a bi-manual I/A system with separate irrigation and aspiration handpieces. These small handpieces can be introduced through two 1.0 mm paracentesis incisions and can easily fit between the two lenses delivering irrigation from one side and aspiration from the opposite side to remove any cortical or inter-lenticular cellular material place a small amount of ProVisc® within the angle of the anterior chamber to stabilize the chamber while allowing for free flow of BSS fluid. Use a straight 27-gauge cannula on a 5cc syringe filled with BSS to vigorously irrigate the space between the two lenses. If for some reason the vigorous irrigation did not remove all the debris from the inter-lenticular space carefully release the haptic/tabs of the IOPCL closest to the location of the debris and continue to irrigate. If this approach is unsuccessful consider removing the IOPCL, irrigate the surface debris on the surface of the PCIOL and replace it with another IOPCL. If the debris attached to the surface of the PCIOL remains adhered after the final attempt to irrigate do not introduce a new IOPCL. At the conclusion of the case, please record in detail on the CRF every and all steps taken to remove the cellular material between the two lenses.

12.1.7. Removal of the IOPCL

The IOPCL is only to be removed for specific causes such as, but not limited to, subject intolerance, damage to the IOPCL and/or base PCIOL, and adverse events being caused by the presence of the IOPCL (e.g., pupillary block or reduced vision).

Removal of the IOPCL will be recorded. **Prior to recording, please ensure that the video equipment is in full working order**. Video recordings will be shared with the Sponsor and FDA.

REMOVAL INSTRUCTIONS:

Re-open the initial incisions or create new access into the anterior chamber if they have healed. With ProVisc in the anterior chamber use a Sinskey hook or similar instrument to disengage the three IOPCL haptics from their respective channels. Place a small amount of ProVisc between the IOPCL and existing PCIOL to separate them apart. Using micro-forceps thru the 2.0 mm wide incision, grasp the anterior and posterior surface of the IOPCL and remove it through the incision. The IOPCL is flexible and will fold and achieve a "taco" form for removal in one piece. After explantation of the complete IOPCL, assess the lens surface of the existing PCIOL for any damage. If any damage is noticed on the existing PCIOL particularly on its lens surface, please record this on the IOPCL removal Case Report Form. Remove the remaining ProVisc, irrigate and close the wound per your normal PCIOL procedures.

Please return the removed IOPCL to the Sponsor for damage assessment.

13. ND:YAG CAPSULOTOMY AFTER IMPLANTATION OF THE PCIOL

An Nd: YAG capsulotomy **is not allowed** to treat opacity between the IOPCL and PCIOL after implanting the IOPCL. Irrigation should be performed to remove the cellular matter from the lens(es) See page 9 for irrigation instructions.

14. EXAMINATION SCHEDULE

Subjects will be examined and evaluated according to the following schedule of visits.

- Form OA Pre-Operative
- Operative (Form OB)
- Form 1 (1 to 2 days postoperative)
- Form 2 (7-14 days postoperative)
- Form 3 (30-60 days postoperative)
- Form 4 (120-180 days postoperative)
- Form 5 (330-420 days postoperative)

14.1. Post-Explantation IOPCL Examination Schedule

Following the removal of the IOPCL subjects will be evaluated according to the following schedule of visits.

- Form 1X (1-2 days post-removal)
- Form 2X (7-14 days post-removal)
- Form 3X (30-60 days post-removal)

- Form 4X (120-180 days post-removal)
- Form 5X (330-420 days post-removal)

14.2. Unscheduled / Interim Visits

Additional visits may be scheduled as deemed necessary by the investigator, to ensure the safety and well-being of the subject.

15. CLINICAL ASSESSMENTS

All parameters will be recorded for both eyes at baseline (pre-operative). Measurements will be recorded for the study eye at postoperative and post-removal visits. See Appendix 2A schedule of visits (pre- and post-operative visits) and Appendix 2B (post-removal visits). See Appendix 3 for clinical assessment instructions.

Order of Clinical Assessments:

- Mesopic contrast sensitivity testing should be performed prior to the slit lamp examination
 and before any visual acuity testing that requires bright light directed at the subject (i.e., a
 reading lamp shined directly over the subject's shoulder onto the reading card).
- Confirmation of IOPCL location should be performed after the study eye is dilated.

Study sites are expected to implement COVID-19 pandemic safety measures in accordance with their local, state, and CDC health guidelines to ensure the health and well-being of the subjects and study staff who come in contact with the subjects.

Clinical Assessments and Timepoints

- Inclusion/exclusion criteria: Preoperative
- Medical history: Preoperative
- External magnifier usage: Preoperative, 30-60 days, 120-180 days, 330-420 days. Interim
 - Post-removal, 30-60 days, 120-180 days, 330-420 days, Interim
- Demographics: Preoperative
- Patient Informed Consent: Preoperative
- Capsulorhexis Size at the time of PCIOL surgery: Preoperative
- Position of PCIOL Haptics and Planned IOPCL Incision Location: Preoperative
- Axial Length: Preoperative
- Keratometry: Preoperative

- Mesopic and Photopic Pupil size measured by Pupillometer: Preoperative.
- Pseudophakic PCIOL power with make and model number: Preoperative.
- Simulation of expected outcome (3.0D lens over manifest refraction at 30cm and 7.0D lens over manifest refraction, at 14cm and preferred distance): Preoperative.
- Ocular Dominance: Preoperative
- Optical Coherence Tomography: Preoperative, 30-60 days, 120-180 days, 330-420 days.
 Interim
 - Post-removal, 30-60 days, 120-180 days, 330-420 days, Interim
- Capsular Stability: Preoperative, Operative, 7-14 days, 30-60 days, 120-180 days, 330-420 days, Interim
 - Post-removal, 7-14 days, 30-60 days, 120-180 days, 330-420 days, Interim
- Spatial Visualization between the PCIOL and IOPCL Using UBM: 30-60 days, 120-180 days, 330-420 days, Interim.
- Recording of the IOPCL Surgical Procedure: Operative
- IOPCL Location and Confirmation of Incision Location: Operative
- IOPCL Location (following dilation): 1-2 days, 7-14 days, 30-60 days, 120-180 days, 330-420 days, Interim
- Manifest Refraction: Preoperative, 7-14 days, 30-60 days, 120-180 days, 330-420 days, Interim
 - Post-removal, 7-14 days, 30-60 days, 120-180 days, 330-420 days, Interim
- Add Power: Pre-Operative, 7-14 days, 30-60 days, 120-180 days, 330-420 days, Interim.
 - Post-removal, 7-14 days, 30-60 days, 120-180 days, 330-420 days, Interim
- BCDVA: Best Corrected Distance Visual Acuity (at 6m) Preoperative, 7-14 days, 30-60 days, 120-18 days, 330-420 days, Interim
 - Post-removal, 7-14 days, 30-60 days, 120-180 days, 330-420 days, Interim
- BCNVA: Best Corrected Near Visual Acuity (at 30 cm (preoperatively); 14 cm (postoperatively) and preferred reading distance (preoperatively and postoperatively)) Pre-Operative, 7-14 days, 30-60 days, 120-180 days, 330-420 days, Interim.
 - Post-removal, 7-14 days, 30-60 days, 120-180 days, 330-420 days, Interim

- UCDVA: Uncorrected Distance Visual Acuity (at 6m)— Preoperative, 7-14 days, 30-60 days, 120-180 days, 330-420 days.
 - Post-removal, 7-14 days, 30-60 days, 120-180 days, 330-420 days. Interim
- UCNVA: Uncorrected Near Visual Acuity (at 14 cm and preferred reading distance) –
 Preoperative, 7-14 days, 30-60 days, 120-180 days, 330-420 days
 - Post-removal, 7-14 days, 30-60 days, 120-180 days, 330-420 days, Interim
- Central Visual Field (Amsler Grid): Preoperative
- Reading Speed (Smith-Kettlewell testing at 40 cm): Preoperative, 7-14 days, 30-60 days, 120-180 days, 330-420 days
 - Post-removal, 7-14 days, 30-60 days, 120-180 days, 330-420 days, Interim
- Contrast Sensitivity (Mesopic): Preoperative, 7-14 days, 30-60 days, 120-180 days, 330-420 days
 - Post-removal, 7-14 days, 30-60 days, 120-180 days, 330-420 days, Interim
- Slit Lamp Examination: Preoperative, 1-2 days, 7-14 days, 30-60 days, 120-180 days, 330-420 days, Interim.
 - Post-removal, 1-2 days, 7-14 days, 30-60 days, 120-180 days, 330-420 days, Interim
- Gonioscopy: 7-14 days, 30-60 days, 120-180 days, 330-420 days, Interim
 - Post-removal, 7-14 days, 30-60 days, 120-180 days, 330-420 days, Interim
- Intraocular Pressure: Preoperative, 1-2 days, 7-14 days, 30-60 days, 120-180 days, 330-420 days, Interim
 - Post-removal, 1-2 days, 7-14 days, 30-60 days, 120-180 days, 330-420 days, Interim
- Dilated Fundoscopy: Preoperative, 7-14 days, 30-60 days, 120-180 days, 330-420 days, Interim
 - Post-removal, 7-14 days, 30-60 days, 120-180 days, 330-420 days, Interim
- Specular Microscopy: Preoperative, 120-180 days, 330-420 days, Interim
 - Post-removal, 120-180 days, 330-420 days, Interim
- VFQ-25 Questionnaire: Preoperative, 30-60 days, 120-180 days, 330-420 days, Interim
 - Post-removal, 30-60 days, 120-180 days, 330-420 days, Interim
- Adverse Events and Complications: Operative, 1-2 days, 7-14 days, 30-60 days, 120-180 days, 330-420 days, Interim

Post-removal, 1-2 days, 7-14 days, 30-60 days, 120-180 days, 330-420 days, Interim

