4.1. Safety Endpoints

- Preservation of BCDVA Proportion of eyes (< 5%) that lose two or more lines of BCDVA (≥10 letters on the ETDRS chart) at 12 months from baseline.
- Preservation of BCNVA Proportion of eyes (<5%) that lose two or more lines of BCNVA
 (≥10 letters on the Sloan Near Vision Chart at 14 cm) at 12 months from baseline.
- Incidence of secondary surgical intervention (SSI).
- Successful delivery of the IOPCL AMD-MAG as determined at all postoperative scheduled visits starting at 7-14 days post-operative.
 - No capsular tear
 - No visible damage to either the PCIOL or the IOPCL AMD MAG
 - o Uniform leaflet coverage of all IOPCL AMD MAG haptic tabs
- Long-term adherence and positional stability
 - O Gap: Minimal change in uniformity of the gap between consecutive scheduled visits at 1-2 months and later as determined by UBM measurements. Minimal change is defined as +/- 10 microns between visits is established and maintained using UBM imaging.
 - o Tilt:
- Tilt of the PCIOL as determined at all post-operative scheduled visits starting at 30-60 days post-operative. Minimal tilt of the PCIOL confirmed via penlight examination and defined as ≤ 10 degrees between the postoperative tilt of the PCIOL and the pre-operative tilt of the PCIOL.
- Tilt of the IOPCL AMD-MAG as determined at all post-operative scheduled visits starting at 30-60 days post-operative. Minimal tilt of the IOPCL AMD-MAG (using the PCIOL as a reference point) confirmed via penlight examination and defined as ≤ 10 degrees between the post-operative tilt of the. PCIOL and the postoperative tilt of the IOPCL AMD-MAG.
- O Decentration: Decentration as determined at all post-operative scheduled visits starting at 7-14 days post-operative. Centration of the IOPCL AMD-MAG (using the PCIOL as a reference point) confirmed during slit lamp examination and defined as uniform exposed area of the PCIOL outside of the IOPCL AMD-MAG at the vertical and horizontal meridians between ≥ 0.25 mm and ≤ 0.75 mm.
- Counts and percentages for incidence of cumulative and persistent intraoperative and post-operative adverse events
- Counts and percentages for incidence of secondary surgical interventions (e.g., removal
 of interlenticular opacity, repositioning of IOPCL, explant of IOPCL, repositioning of
 PCIOL) (excluding Nd:YAG treatments for PCO).

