5.1. Inclusion Criteria

- 1. Subjects aged 55 years or older.
- 2. Subjects who have already had cataract surgery with an Alcon SN60WF, SA60AT or SA60WF monofocal intraocular lens with a lens power between 17.0 diopters and 24.0 diopters clearly evidenced by photographic documentation by one of the following:
 - patient medical record
 - clinic chart with labeling attached
 - surgical record with labeling attached, or
 - patient identification card with make, model and serial number.
- 3. Subjects who have already had cataract surgery at least 6 months from the planned date of the IOPCL surgery.
- 4. Subjects with non-neovascular dry AMD or stable wet AMD meeting the following criteria:
 - No macular fluid retention in the past 12 months
 - No treatment within the past 12 months
 - No change in Amsler Grid test within the past 12 months
 - No subretinal fluid or macular hemorrhage confirmed by optical coherence tomography (OCT) imaging.
 - No fundoscopic changes within the past 12 months (i.e., changes in retinal pigment epithelium).
- 5. Subjects with best corrected distance visual acuity from 20/80 to 20/800.
- 6. Subjects with a preoperative manifest refraction spherical equivalent (MRSE) of +1.0D to -1.0D.
- 7. Subjects with ≤1.0D of corneal cylinder determined by keratometry readings.
- 8. Subjects who are unsatisfied with their current near vision correction provided by either spectacles or external magnifier.
- 9. Subjects who have experienced and failed one or more high-magnification refractive correction alternatives to the IOPCL AMD-MAG.

- 10. Subjects who demonstrate at least 10 letters of near visual acuity improvement with the simulation/tolerance test (using manifest refraction with +7.0D add) compared to conventional near vision testing (using manifest refraction with +3.0D add).
- 11. Subjects with a minimum endothelial cell count of 1800 cells/mm².
- 12. Subjects willing to abstain from pursuing any other surgical vision-correcting procedures for the duration of the study.
- 13. Subjects who are willing and able to complete all required postoperative visits.
- 14. Subjects who are able to comprehend and sign a statement of informed consent.

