# 3.2 Safety Endpoints

• Preservation of Best Corrected Distance Visual Acuity (BCDVA)

The preservation of BCDVA is defined as proportion of eyes (< 5%) that lose two or more lines (≥10 letters) of BCDVA at 12 months from baseline.

• Preservation of Best Corrected Near Visual Acuity (BCNVA)

Proportion of eyes (<5%) that lose two or more lines of BCNVA (≥10 letters on the Sloan Near Vision Chart at 14 cm) at 12 months from baseline.

- Incidence of secondary surgical intervention (SSI)
- Successful Delivery of the IOPCL as determined as all postoperative scheduled visits starting at 7-14 days postoperative.

The successful delivery of the IOPCL is defined as no capsular tear, no visible damage to either the IOL or IOPCL, and uniform leaflet coverage of all IOPCL haptic tabs.

• Long-term Adherence and Positional Stability

The long-term adherence and positional stability is defined as 1) minimal change in uniformity of the gap between consecutive scheduled visits at 1-2 months and later as determined by UBM imaging (where minimal change is defined as +/- 10 microns between visits established and maintained using UBM imaging).

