# 6.2 Sample Size

Sample size is limited to maximum of 10 subjects (eyes) for this Early Feasibility Study (EFS).

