# 6.5 Handling of Dropouts and Missing Data

All data analyses will be conducted based on available data. No imputation will be performed.

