## 7.5.1 Preservation of BCDVA

The analysis of this clinical outcome will be based on the observed data of IOPCL AMD-MAG. The number and percent of IOPCL implanted eyes with a BCDVA loss of 2 or more lines (≥10 letters) at 12 months from preoperative will be derived.

Additionally, if needed, data listing or summary will be provided for eyes with a BCDVA loss of  $\geq 2$  lines from the best BCDVA before the corresponding visits.

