## 7.5.7 Other Safety Analyses

## 7.5.7.1 Best-corrected Distance Visual Acuity

All the available monocular best-corrected distance visual acuity at each protocol specified scheduled visit will be presented for the implanted eyes. The categorical presentations will include the visual acuity of 20/16 or better, 20/20 or better, 20/25 or better, 20/32 or better, 20/40 or better, 20/50 or better, 20/63 or better, 20/80 or better, and worse than 20/80.

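### Only 6 m is given for best corrected distance acuity while eyes down to 20/800 are eligible; unless Appendix 3 says otherwise, a 10-letter loss may go unrecorded in the worst eyes

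*Protocol*

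**What the plan says.** The list of assessments in Protocol Section 15 gives the test as "BCDVA: Best Corrected Distance Visual Acuity (at 6m"). No second distance is offered, whereas the near-acuity entries in the same list add the subject's preferred reading distance. The section refers to Appendix 3 for the clinical methods.

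Inclusion criterion 5 (Protocol 5.1) reads: "Subjects with best corrected distance visual acuity from 20/80 to 20/800".

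The first safety endpoint in Protocol 4.1 is the proportion of eyes that "lose two or more lines of BCDVA (≥10 letters on the ETDRS chart) at 12 months from baseline". SAP 3.2 repeats the limit: "The preservation of BCDVA is defined as proportion of eyes (< 5%) that lose two or more lines". SAP 7.5.1 states what is calculated, in a sentence that opens "The number and percent of IOPCL implanted eyes with a BCDVA loss of 2 or more lines (≥10 letters) at 12 months from preoperative will". SAP 6.5 adds: "All data analyses will be conducted based on available data. No imputation will be performed". Neither document states the largest line on the chart or how an eye that reads no letters is scored.

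The descriptive BCDVA table in SAP 7.5.7.1 ends with the categories "20/63 or better, 20/80 or better, and worse than 20/80".

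**The concern.** A loss of 10 letters can be recorded only in an eye that reads at least 10 letters at baseline. The eligibility range reaches far down the acuity scale, and the only stated test distance is the one at which very poor acuity is hardest to measure. The eyes with least visual reserve may therefore be unable to show the event.

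The endpoint is the first safety endpoint and the study has at most 10 eyes, so one unrecorded loss can change the reported result. Other parts of the plan add to the risk. Where both eyes qualify, Protocol Section 8 selects the one with more pathology, which plausibly moves enrolment towards the floor. In the SAP 7.5.7.1 table, every eligible eye except one at exactly 20/80 starts in the lowest category, so that table cannot reveal further loss either. The additional listing in SAP 7.5.1 is optional and uses the same two-line measure.

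**Working it through.** The documents give no chart range and no power figure for this endpoint, so there is no stated number to reproduce.

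**Inputs from the documents.** Test distance 6 m (Protocol 15); eligible range 20/80 to 20/800 (Protocol 5.1); event of 10 or more letters, equal to two lines, so 5 letters per line (Protocol 4.1); limit of under 5% (Protocol 4.1, SAP 3.2); at most 10 eyes (SAP 6.2).

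**Assumptions.** Each line is 0.1 logMAR. The chart's largest line at 6 m is 20/X, with X varied from 200 to 1000.

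**Step 1: letter size at 6 m.** A 20/20 letter subtends 5 arcmin, so a 20/D letter subtends 5 × D/20 arcmin. Height = 2 × 6000 mm × tan(half that angle).
- 20/800: 200 arcmin, 349 mm. Five letters with four letter-wide gaps span 9 × 349 mm = 3.14 m.
- 20/1000: 250 arcmin, 437 mm, and a line 3.93 m wide.

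**Step 2: worst baseline that can show the event.** An eye that reads only the top line scores 5 letters, and one that reads the top two lines scores 10 and can fall to 0. The worst usable baseline is therefore one line better than the top line, with denominator X/10^0.1. For a baseline of 20/800 this requires X = 800 × 10^0.1, about 1007, hence a top line of about 20/1000.

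**Step 3: share of the eligible range that cannot show the event.** The range is log10(800/80) = 1.0 logMAR, or 50 letters. Share = log10(800 ÷ (X/10^0.1)) ÷ 1.0.

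| Assumed top line at 6 m | Worst baseline able to lose 10 letters | Share of eligible logMAR range below it |
|---|---|---|
| 20/200 | 20/159 | 70% |
| 20/400 | 20/318 | 40% |
| 20/800 | 20/635 | 10% |
| 20/1000 | about 20/800 | about 0% |

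These are shares of an acuity interval. The documents give no distribution of baseline acuity, so they do not translate into numbers of eyes.

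**Step 4: effect on the endpoint.** One loss among 10 eyes is 10%, so under 5% means zero losses. The same holds for any smaller number of evaluable eyes. Suppose k of 10 eyes are at the floor and are either counted as preserved or dropped as missing. With true loss rate p, the chance of observing no loss is (1 − p)^(10 − k).

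| True loss rate | k = 0 | k = 3 | k = 5 |
|---|---|---|---|
| 5% | 0.60 | 0.70 | 0.77 |
| 10% | 0.35 | 0.48 | 0.59 |
| 20% | 0.11 | 0.21 | 0.33 |

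Both k and p are illustrative.

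**Step 5: would a shorter distance be enough?** This depends on the chart. If the top line is 20/200 at a design distance of 4 m, then at 1 m it is 200 × 4/1 = 20/800. An eye at 20/800 then reads about 5 letters and still cannot lose 10. If the design distance is 6 m, the top line at 1 m is 20/1200 and the same eye reads about 14 letters. A score for off-chart vision is therefore also needed.

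**The case against.** The strongest objection is that Section 15 is a timetable and the method is in Appendix 3, which is not in the available text. A reduced-distance procedure and a scoring rule for unread charts would naturally be found there, and a sponsor that sets a limit of 20/800 presumably has a way to measure it. This stands, and it makes the point conditional. It does not remove it: Section 15 names one distance, and if that distance is followed it does not fit the eligibility range and the endpoint.

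A reader might infer that the loss cannot be recorded at all and that the endpoint is biased towards passing. The documents do not support that. They neither forbid another distance nor say how off-chart vision is handled. Floored eyes scored near zero and counted as preserved would favour meeting the limit, and eyes treated as missing under the no-imputation rule could also hide a loss. A rule that counted an off-chart result as a loss would not favour meeting it.

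A reader might also require the eye still to read the top line after losing two lines, which would give 80%, 50% and 20% for the three top lines from 20/200 to 20/800. The endpoint is scored in letters, so a fall from 10 letters to none counts, and 70%, 40% and 10% are the right shares.

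Finally, this is an early feasibility study that reports a count and percentage without a test. Serious loss could also surface through sight-threatening adverse events, the stopping rule on permanent impairment, OCT or fundoscopy. That is fair, and it limits the consequence. None of these routes replaces a letter-based endpoint.

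**Conclusion.** The concern holds in conditional form. The stated 6 m distance does not fit eligibility down to 20/800 and an endpoint of 10 or more letters lost. By geometry, letter scoring over the whole range at 6 m would need letters about 44 cm high in a line nearly 4 m wide, which is impractical. Unless Appendix 3 provides otherwise, an eye with fewer than 10 letters at baseline cannot register the event.

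The affected share of the eligible logMAR range is about 70%, 40% or 10% for an assumed top line of 20/200, 20/400 or 20/800. If affected eyes are counted as preserved or dropped, the limit becomes easier to meet: with a true loss rate of 10% and three such eyes, the chance of zero recorded losses rises from 0.35 to 0.48. The size in this trial depends on the chart, the off-chart handling and the number of enrolled eyes near the floor, none of which the available text gives. Meeting the limit is a descriptive result, not a hypothesis test.

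**What to change.** In Protocol Section 15, aligned with Appendix 3:
- State the chart's range and a reduced test distance for eyes that read fewer than a set number of letters at 6 m.
- Use the same distance for that eye at baseline and every later visit, adjust the refraction for the distance (6 m to 1 m changes vergence by 1/1 − 1/6 = 0.83 D), and convert all results to one letter scale.

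In SAP 7.5.1:
- Pre-specify a score for off-chart vision and count a fall from on-chart to off-chart as a loss. This is conservative for an eye with fewer than 10 letters at baseline, which could be counted after a smaller loss.
- Report the distance used for each eye and flag eyes with fewer than 10 letters at baseline, so that a reader can see which eyes could not show a 10-letter fall.

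In SAP 7.5.7.1, add categories below 20/80 that cover the eligible range and beyond it.

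If Appendix 3 already contains these rules, Section 15 needs only a matching sentence and the SAP its scoring rule, flags and categories. The cost is protocol and SAP wording and a few extra minutes of testing, including the refraction adjustment, for some eyes.
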